6.5.3 Rescue medication

Not applicable.

6.6 Dose modification

No PSL dose modifications are permitted during the study for an individual study participant unless necessary to protect study participant safety or well-being.

6.7 Treatment after the end of the study

There are no plans for participant treatment after the end of the study.

7 DISCONTINUATION OF STUDY MEDICATION AND PARTICIPANT DISCONTINUATION/WITHDRAWAL

7.1 Discontinuation of study medication

Study medication will be stopped if the study participant develops a medical condition (or laboratory abnormality or ECG change) that, in the opinion of the Investigator, compromises the study participant's ability to participate or compromises the study participant's safety.

[figure not shown]
In all cases, the study participant should be followed until the condition has resolved as agreed by the Investigator and the UCB Study Physician. If a participant discontinues study medication, no restart will be allowed.

7.1.1 Liver chemistry stopping criteria

Discontinuation of study medication for abnormal liver function should be considered by the Investigator when a participant meets 1 of the conditions outlined for potential drug-induced liver injury (PDILI) outlined in [Figure 7-1](#) or if the Investigator believes that it is in best interest of the study participant.

Study medication will be discontinued immediately and permanently for a study participant if liver chemistry stopping criteria are met.

Figure 7-1: Liver chemistry stopping algorithm

ALT=alanine aminotransferase; AST=aspartate aminotransferase; INR=international normalized ratio; SAE=serious adverse event; ULN=upper limit of normal

Specific assessments and follow up actions for potential drug-induced liver injury are provided in Appendix 6 (Section 10.6). Discontinuation of study medication for abnormal liver function should be considered by the Investigator when a study participant meets 1 of the conditions outlined in the algorithm or if the Investigator believes that it is in best interest of the study participant.

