 - Participant has active suicidal ideation with a specific plan as indicated by a positive response ("Yes") to Question 5 of the "Since Last Visit" version of the C-SSRS. The study participant should be referred immediately to a mental healthcare professional and must be withdrawn from the study.
9. Study participant is suspected of having a serious multiorgan hypersensitivity reaction. Serious suspected multiorgan hypersensitivity cases may be identified and reported to the Sponsor by the Investigator using the following algorithm:
 - An AE or laboratory value (as defined below) suggestive of internal organ involvement including but not limited to hepatitis, nephritis, pneumonitis, carditis, colitis, encephalitis, pancreatitis, myositis, arthritis, or hematologic system involvement combined with at least 1 of the following: fever, rash, lymphadenopathy, or eosinophilia.
 - Treatment-emergent abnormal laboratory value criteria suggestive of internal organ involvement or eosinophilia:
 - Eosinophils percentage $\geq 10\%$.
 - Eosinophils absolute $\geq 0.5\text{G/L}$.

- Neutrophils absolute <1.5G/L.
- Platelets absolute \leq 100G/L.

Withdrawn study participants should follow the Taper schedule if possible, unless faster discontinuation is considered necessary in the medical judgement of the Investigator. Investigators should attempt to obtain information on study participants in the case of withdrawal.

Investigators should contact the UCB Study Physician, whenever possible, to discuss the withdrawal of a participant in advance.

Participants withdrawn may be replaced at the discretion of the Investigator and Sponsor.

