8.5.6 AESI

An AESI is any AE that a regulatory authority has mandated be reported on an expedited basis, regardless of the seriousness, expectedness, or relatedness of the AE to the administration of a UCB product/compound. No AESIs have been identified for PSL to date, with the exception of potential Hy's Law as described below.

Potential Hy's Law, defined as $\geq 3 \times \text{ULN}$ ALT or AST with coexisting $\geq 2 \times \text{ULN}$ total bilirubin in the absence of $\geq 2 \times \text{ULN}$ ALP, with no alternative explanation for the biochemical abnormality,

must ALWAYS be reported to UCB as an AESI (ie, without waiting for any additional etiologic investigations to have been concluded). Follow-up information should then be reported if an alternative etiology is identified during investigation and monitoring of the participant.

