^b Details of liver chemistry stopping criteria and required actions and follow-up assessments after liver stopping or monitoring event are given in Section 7.1.1 and Section 10.6. All events of ALT \geq 3XUL and bilirubin \geq 2XULN ($>35\%$ direct bilirubin) or ALT \geq 3XULN and INR >1.5 , if INR measured, may indicate severe liver injury (possible Hy's Law) and must be reported as an SAE (excluding studies of hepatic impairment or cirrhosis).

^c Local urine testing will be standard for the protocol unless serum testing is required by local regulation or IEC. Serum pregnancy test will be performed at Screening.

The Investigator must document their review of each laboratory safety report.

Laboratory/analyte results that could unblind the study will not be reported to the investigative site or other blinded personnel until the study has been unblinded.

REDACTED COPY
This document cannot be used to support any marketing authorization application and any extensions or variations thereof.

10.3 Appendix 3: Adverse Events – Definitions and Procedures for Recording, Evaluating, Follow-up, and Reporting

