10.6 Appendix 6: Liver safety – Suggested Actions and Follow-up Assessments

Study participants with PDILI must be assessed to determine if study medication must be discontinued. In addition, all concomitant medications and herbal supplements that are not medically necessary should also be discontinued.

Investigators should attempt to obtain information on study participants in the case of study medication discontinuation to complete the final evaluation.

Study participants with PDILI should not be withdrawn from the study until investigation and monitoring are complete. All results of these evaluations and observations, as well as the reason(s) for study medication discontinuation and/or study participant withdrawal (if applicable), must be recorded in the source documents. The eCRF must document the primary reason for discontinuation of study medication.

A specific monitoring plan must be agreed between the UCB Study Physician and the Investigator for study participants who have ALT >3 ULN. The monitoring plan should include any necessary follow-up assessments (until resolution of the abnormal lab values).

Phase 1 liver chemistry stopping criteria are designed to assure study participant safety and to evaluate liver event etiology (see [Table 10-3](#)).

Table 10-3: Phase I liver chemistry stopping criteria and follow-up assessments

Liver chemistry stopping criteria	
ALT-absolute ALT \geq 3xULN If ALT \geq 3xULN AND bilirubin \geq 2xULN (>35% direct bilirubin) OR INR >1.5, report as an SAE ^{a,b} See additional actions and follow-up assessments listed below	
Required actions and follow-up assessments	

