^a All events of $ALT \geq 3 \times ULN$ and bilirubin $\geq 2 \times ULN$ ($> 35\%$ direct bilirubin) or $ALT \geq 3 \times ULN$ and $INR > 1.5$ may indicate severe liver injury (**possible 'Hy's Law'**) and **must be reported as an SAE (excluding studies of hepatic impairment or cirrhosis)**. The INR measurement is not required and the stated threshold value will not apply to study participants receiving anticoagulants.

^b Serum bilirubin fractionation should be performed if testing is available. If serum bilirubin fractionation is not immediately available, discontinue study intervention if $ALT \geq 3 \times ULN$ and bilirubin $\geq 2 \times ULN$. Additionally, if serum bilirubin fractionation testing is unavailable, **record the absence/presence of detectable urinary bilirubin on a dipstick**, which is indicative of direct bilirubin elevations suggesting liver injury.

^c Hepatitis A IgM antibody; HBsAg and HBcAb; hepatitis C RNA; cytomegalovirus IgM antibody; Epstein-Barr viral capsid antigen IgM antibody (or if unavailable, heterophile antibody or monospot testing); and hepatitis E IgM antibody.

**10.7 Appendix 7: Medical Device Incidents – Definition and
Procedures for Recording, Evaluating, Follow up, and
Reporting**

Not applicable.

REDACTED COPY
This document cannot be used to support any marketing authorization application and any extensions or variations thereof.

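### Liver rules: the protocol leaves open whether an isolated ALT ≥3×ULN mandates stopping, and it uses two different sets of criteria for potential Hy's Law

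*Protocol*

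**What the plan says.** **Stopping.** Section 7.1.1 opens by saying that discontinuation for abnormal liver function "should be considered by the Investigator when a participant meets 1 of the conditions outlined for potential drug-induced liver injury", and points to Figure 7-1. The next sentence says "Study medication will be discontinued immediately and permanently for a study participant if liver chemistry stopping criteria are met". After the figure, which is titled as the liver chemistry stopping algorithm, the text again asks the Investigator to consider discontinuation when one condition of that algorithm is met.

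Appendix 6 (Section 10.6) begins: "Study participants with PDILI must be assessed to determine if study medication must be discontinued". Its Table 10-3 then puts ALT ≥3×ULN under a heading of stopping criteria.

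**Potential Hy's Law.** Section 8.5.6 defines it as ALT or AST ≥3×ULN with total bilirubin ≥2×ULN, no ALP ≥2×ULN and no alternative explanation. Such a case "must ALWAYS be reported to UCB as an AESI". Footnote b of Table 10-1 (Appendix 2), and Table 10-3 with its footnote a (Appendix 6), use ALT ≥3×ULN only, with either bilirubin ≥2×ULN (more than 35% direct) or INR >1.5. They require the event to be reported as an SAE. Appendix 3 (Section 10.3.2) names potential Hy's law as an example of an important medical event, a class it says is usually to be treated as serious.

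**Study hold.** Under Section 7.1.3, one SAE at least possibly related to study medication puts the study on temporary halt. Restart needs an approved substantial amendment.

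**The concern.** A stopping rule should give the same answer whichever paragraph the site reads. Here a participant with ALT ≥3×ULN and nothing else abnormal meets a listed stopping criterion, so one sentence requires permanent discontinuation. Two other sentences in the same section, and the opening of Appendix 6, leave the outcome to assessment.

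The second issue is classification. Two definitions of what is meant to be the same liver signal differ in the transaminase used, the bilirubin fraction, INR, ALP and the alternative-cause condition. SAE status feeds the study hold, so it should not depend on which section was consulted. These are healthy participants who receive no medical benefit (Section 2.3), which is a further reason for the instruction to be unambiguous.

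**Working it through.** No sample size, error rate or event count enters this point, so there is nothing to recompute. The check sets the passages side by side.

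**Step 1. Isolated ALT ≥3×ULN (bilirubin <2×ULN, INR ≤1.5).**

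- Table 10-3: a stopping criterion is met.
- Section 7.1.1, second sentence: stop at once and permanently.
- Section 7.1.1, first sentence and the text after the figure: if the result is a condition of the algorithm, the Investigator considers stopping.
- Appendix 6, opening: if the case counts as potential drug-induced liver injury, it is assessed to decide whether stopping is needed.

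Nothing in the text says which of these governs.

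**Step 2. When the question can arise.** Table 1-1 schedules clinical chemistry at Screening, Day -1, Day 14 and the Safety Follow-up Visit. Dosing runs from Day 1 to Day 11, so the Day 14 sample is 14 − 11 = 3 days after the last dosing day. No scheduled sample falls on a dosing day. With three Treatment Periods there are two transitions (1 to 2, and 2 to 3). The live cases are therefore Day 14 of Periods 1 and 2, Day -1 of Periods 2 and 3, and any unscheduled test during dosing.

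**Step 3. Patterns that the two sets of Hy's Law criteria classify differently.**

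| Pattern | Section 8.5.6 (AESI) | Appendices 2 and 6 (SAE) |
|---|---|---|
| A. AST ≥3×ULN, ALT <3×ULN, bilirubin ≥2×ULN, ALP <2×ULN, no other cause | Met | Not met (ALT only) |
| B. ALT ≥3×ULN, bilirubin ≥2×ULN with ≤35% direct, INR ≤1.5, ALP <2×ULN, no other cause | Met | Not met (direct fraction) |
| C. ALT ≥3×ULN, INR >1.5, bilirubin <2×ULN | Not met (bilirubin) | Met |
| D. ALT ≥3×ULN, bilirubin ≥2×ULN with >35% direct, ALP ≥2×ULN | Not met (ALP) | Met |

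**Step 4. Consequence for the hold.** Patterns C and D are SAEs by explicit rule, and nothing in 8.5.6 removes that status. The disagreement there is only whether the AESI report is also due. Patterns A and B fall outside the explicit SAE rule. They become SAEs through the important-medical-event example in Appendix 3, which is framed as a matter of medical or scientific judgement. If judged serious and at least possibly related, one such case triggers the hold in 7.1.3. If not judged serious, it does not trigger the SAE limb of the hold.

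**The case against.** The best defence of Section 7.1.1 is a two-tier reading: potential drug-induced liver injury in Figure 7-1 prompts consideration, while the narrower criteria of Table 10-3 mandate a stop. The figure is not reproduced in the copy reviewed, and its legend mentions AST and INR, so it may well be wider than the ALT criterion. This reading is possible, and the absent figure is not held against the plan. But no sentence states the two tiers, and the discretionary sentences refer to the figure that carries the stopping title.

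Three stronger readings may tempt a reader, and the protocol does not support them.

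- *That AESI and SAE are alternative classes, so a case under 8.5.6 escapes the hold.* Section 8.5.6 makes an AESI reportable whatever its seriousness, so one event can be both. Appendix 3 uses the same label as 8.5.6 (potential rather than possible Hy's Law), which favours treating those cases as usually serious. What remains is that patterns A and B depend on a judgement where C and D have an explicit rule.
- *That footnote b of Table 10-3 orders a stop only when bilirubin is raised.* It reads "If serum bilirubin fractionation is not immediately available, discontinue study intervention if" ALT is ≥3×ULN and bilirubin ≥2×ULN. It covers a missing fractionation result and is attached to the SAE reporting line. It does not narrow the ALT criterion.
- *That an immediate liver stop contradicts the taper instruction.* Section 7.2 says "Withdrawn study participants should follow the Taper schedule if possible", but the same sentence allows faster discontinuation on the Investigator's medical judgement. It also concerns participants withdrawn from the study, and Appendix 6 keeps liver-injury cases in the study until their investigation is complete.

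It is also fair that the practical reach is small, given the chemistry schedule in Table 1-1.

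**Conclusion.** The point stands as two wording inconsistencies in current operative text.

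1. For an isolated ALT ≥3×ULN, Section 7.1.1 and Appendix 6 support both a mandatory stop and a judgement. This matters mainly for entry into the next Treatment Period and for unscheduled tests during dosing.
2. Potential Hy's Law has two sets of criteria. At least four laboratory patterns are classified differently, and two of them (AST-driven, and low direct bilirubin) reach SAE status only through the general wording of Appendix 3. One related case of either kind is enough for the answer to bear on the study hold.

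The first conclusion assumes that the unseen figure does not itself spell out two tiers. If it does, the text should still say so. The second does not depend on the figure. Neither affects the primary QTc analysis or the sample size. The protocol should be corrected because the passages direct participant safety and the correction is cheap. No view is taken on which clinical rule is right.

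**What to change.** Reconcile Section 7.1.1 with Appendix 6 so that it is explicit which liver results mandate discontinuation and which prompt Investigator assessment. Use the same terms in the text, Figure 7-1 and Table 10-3.

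Align the potential Hy's Law criteria and the reporting instruction across Section 8.5.6 and Appendices 2, 3 and 6. State whether every such case is reported as both an AESI and an SAE, so that its bearing on the hold in Section 7.1.3 is clear.

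The choice of thresholds and rules is for the sponsor's clinical team, and none is proposed here. The cost is protocol wording only, with no extra tests, visits or participants.

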7.1.2 QTc stopping criteria

A participant who meets the bulleted criteria based on the average of triplicate ECG readings will be withdrawn from the study.

- QTc $> 500\text{ms}$
- Change from Baseline: QTc $> 60\text{ms}$

See the Schedule of activities (Table 1-1) for data to be collected at the time of treatment discontinuation and follow up and for any further evaluations that need to be completed.

7.1.3 Study hold/stopping rules

In recognition of the advanced status of the development program for PSL, the following study hold/stopping rules will apply to this study:

- A serious adverse reaction (SAR) (ie, an SAE considered at least possibly related to the study medication) in 1 study participant;
- A severe nonserious adverse reaction (ie, severe nonserious AEs considered at least possibly related to the study medication administration) in 2 study participants in the same cohort, independent of within or not within the same SOC.

If either stopping criterion is met, the study will be put on temporary halt. In the event that either or both of the stopping criteria are met, a safety review will be immediately initiated. The safety review will be conducted by an internal, study-specific Safety Monitoring Committee comprised of the Investigator and appropriate members of the UCB Study Team (such as Study Physician, Safety Physician, Clinical Project Manager, Clinical Pharmacologist), as quickly as possible, to review the available data and determine whether it is appropriate to continue dosing at the next scheduled dosing point. This will take the form of a risk/benefit evaluation from the perspective of the individual study participants. In making this evaluation, account will be taken of the potential risks of sudden discontinuation of study medication, particularly in participants who may be taking higher dose levels, and whether or not a tapering period, and its duration/speed, should be undertaken.

The Safety Monitoring Committee will also decide whether it is appropriate to continue the study with or without dose adaptations, additional safety assessments, or other changes in design. In case of any temporary halt of the study, further dosing in the study will be suspended while a substantial amendment is submitted to the Country(ies) Health Authority and Research Ethics Committee(s) and the study will not restart until that amendment has been approved.

Detailed procedures for reporting SAEs and other safety events which may meet study hold/stopping criteria are provided in Appendix 3 (see Section Section 10.3).

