4.1.1 Screening and Baseline Periods

The design uses a 3-Treatment Period crossover structure. Study participants who provide written informed consent will be screened within 28 days before the first Treatment Period. For further details regarding the assessments performed during the Screening and Baseline Periods, refer to the Schedule of activities ([Table 1-1](#)).

4.1.2 Treatment Periods 1, 2, and 3

During each Treatment Period, each study participant will check into the site the day prior to the relevant First Dosing Day. Throughout the relevant Dosing Days, continuous Holter monitoring will be undertaken to provide extracted ECG records at the relevant time points necessary to the evaluation of QT interval effects. During the hour prior to administration of the first dose of each Treatment Period, 3 triplicate ECGs extracted from the Holter record will serve to provide a time-averaged Baseline for that Treatment Period.

Subsequently, dosing with the allocated study medication will be initiated: for study participants in the PSL Treatment Period, the bid doses of PSL will be titrated up to reach steady state in time for the target dose on the 'Target Dose Day,' as shown in [Figure 1-1](#).

The randomized dosing regimen will be as follows:

- In the PSL Treatment Period:
 - On Day 1, 100mg PSL will be administered bid, in the morning and the evening.
 - On Days 2 and 3, 200mg PSL will be administered bid, in the morning and the evening.
 - On Days 4 and 5, 300mg PSL will be administered bid, in the morning and the evening.
 - On Days 6 and 7, 400mg PSL will be administered bid, in the morning and evening.
 - On Day 8, the Target Dose Day, study participants will be fasted prior to the morning dose. Subsequently, 400mg PSL will be administered in the morning, and placebo will be administered in the evening.
 - On Day 9, 300mg PSL will be administered bid, in the morning and the evening.

- On Day 10, 200mg PSL will be administered bid, in the morning and the evening.
- On Day 11, 100mg PSL will be administered bid, in the morning and the evening.
- In the Placebo Treatment Period:
 - On Days 1 through 7, placebo to match the PSL Treatment Period doses will be administered bid, in the morning and the evening.
 - On Day 8, the Target Dose Day, study participants will be fasted prior to the morning dose. Subsequently, placebo to match 400mg PSL will be administered in the morning, and in the evening.

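### Section 7.1.3 counts severe reactions within a cohort that this crossover never defines, and its dosing suspension conflicts with the committee's power, in the same section, to continue or taper dosing

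*Protocol*

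**What the plan says.** All of the following are in the protocol.

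- **Triggers (Section 7.1.3).** Trigger 1 is a serious adverse reaction in one participant. Trigger 2 is a severe nonserious adverse reaction "in 2 study participants in the same cohort", whether or not the events share a system organ class.
- **Consequence (Section 7.1.3).** "If either stopping criterion is met, the study will be put on temporary halt".
- **Committee's task (Section 7.1.3).** The Safety Monitoring Committee is to "determine whether it is appropriate to continue dosing at the next scheduled dosing point". It must weigh the danger of stopping abruptly, especially at higher doses, and decide "whether or not a tapering period, and its duration/speed, should be undertaken".
- **Suspension (Section 7.1.3).** In any temporary halt, "further dosing in the study will be suspended while a substantial amendment is submitted", and the study restarts only after that amendment is approved.
- **Design (Section 4.1.1).** "The design uses a 3-Treatment Period crossover structure".
- **Scheduled taper (Section 4.1.2).** "On Day 9, 300mg PSL will be administered bid, in the morning and the evening". Day 10 is 200mg bid. "On Day 11, 100mg PSL will be administered bid, in the morning and the evening".
- **Known hazard (Section 2.3).** Two healthy participants had acute psychiatric serious events early after starting or stopping PSL without titration or taper. Gradual titration and taper are named as the mitigation.

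**The concern.** A mandatory hold rule should give the same answer to everyone who applies it.

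The cohort wording limits trigger 2 to some unit, but the protocol does not say which. It could mean all participants, a treatment sequence, an admission group, or those on the same treatment or in the same period. Two people could disagree in good faith on whether the study must stop.

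The suspension sentence has a different problem. A taper dose is a dose. Taken at its word, the sentence leaves the committee nothing to decide about continued dosing or taper, although the section has just given it both decisions. Dosing is twice daily, so the question could arise within about half a day of a trigger. What is at stake is whether people on up to 400mg bid are stepped down or stopped abruptly.

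**Working it through.** The check is mainly textual. The protocol gives no figure for this rule to reproduce.

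**Step 1: what could 'cohort' refer to?**

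- Sections 4.1, 4.1.1 and 4.2 describe one single-center randomized crossover. Section 1.1 gives up to 54 randomized participants.
- The word appears only in trigger 2 and is not defined.
- Trigger 1 has no such limit. If trigger 2 meant the whole study, the limiting words would be unnecessary.

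**Step 2: the sentences of Section 7.1.3 in order.**

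| Order | Content | Dosing allowed? |
|---|---|---|
| 1 | Either trigger puts the study on temporary halt | Not stated |
| 2 | Committee decides on dosing at the next dosing point | Possibly |
| 3 | Committee weighs abrupt stopping and whether to taper | Taper possible |
| 4 | Any temporary halt suspends further dosing until an amendment is approved | No, without exception |

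Row 1 means that every committee review takes place within a temporary halt. Row 4 applies to every temporary halt. Rows 2 and 3 therefore have effect only if row 4 carries an exception that it does not state.

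**Step 3: does another section supply the exception?**

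- Section 6.6 allows an individual's PSL dose to be modified for safety.
- Section 7.2 asks withdrawn participants to follow the taper if possible, but a halt does not by itself withdraw anyone.
- Section 10.1.1 allows changes without prior ethics approval to remove an immediate hazard.
- Sections 7.1 and 7.1.4 bar a restart after discontinuation, so a taper begun after suspended doses could be questioned.

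The first three support a taper. None says that taper doses are outside the suspension.

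**Step 4: size on the literal reading.** The inputs are the Section 4.1.2 doses: 300, 200 and 100mg bid on Days 9, 10 and 11.

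- Doses: 3 days × 2 = 6.
- Amount: 2 × (300 + 200 + 100) = 1,200mg.

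This full amount applies only to a participant halted after the Day 8 morning dose and before Day 9. After Day 9 the remainder is 2 × (200 + 100) = 600mg in 4 doses. After Day 10 it is 2 × 100 = 200mg in 2 doses. A participant in the placebo or moxifloxacin period has no PSL taper to lose.

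**The case against.** The strongest reply is that the taper is already provided for. The committee's evaluation happens only after a trigger, so its taper instruction can only operate during a halt. A reading that leaves that instruction no work to do is unlikely to be the intended one. This stands as evidence of intent, and it is the main reason the point is minor. It does not remove the conflict, because the suspension sentence is the later and unqualified one.

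A second reply separates two levels: the committee first handles individual participants, and the study-level suspension follows. That gives every sentence a role. But it is an inference. The halt starts when a trigger is met, and the suspension covers any halt, so the text does not place the suspension after the individual decisions.

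A third reply is that, with no narrower unit defined, all participants is the natural and more protective default for 'cohort'. That is fair, and it is probably what was meant. The rule should say so.

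A reader might infer more than the documents support:

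- **That the plan requires abrupt withdrawal from 400mg bid.** It does not. The taper instruction in Section 7.1.3 and Sections 6.6, 7.2 and 10.1.1 point the other way.
- **That the undefined cohort changes the chance of a halt by a known amount.** The protocol gives neither a cohort size nor a rate of severe related reactions for this titrated regimen. Section 4.3 mentions 9 PSL-treated participants with severe events, but does not give their relatedness.
- **That the 2 psychiatric cases show harm from stopping.** Section 2.3 does not split them between starting and stopping.

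**Conclusion.** Both wording defects hold, at low severity. Trigger 2 is limited to a unit this design does not have. The closing suspension conflicts with the committee's dosing and taper decisions in the same section. The likely intent is a count over all participants and a committee-directed taper during a halt.

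The upper bound of 6 doses and 1,200mg per participant rests on two assumptions: that the suspension is read literally, and that the halt falls between the Day 8 morning dose and Day 9. The practical risk is smaller, because the Investigator sits on the committee and other sections support tapering. The point is worth correcting because Section 2.3 itself names taper as a mitigation for acute psychiatric events.

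**What to change.** Three wording changes in Section 7.1.3:

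1. In trigger 2, replace 'in the same cohort' with 'in the study'.
2. Keep the suspension, but exempt taper doses that the Safety Monitoring Committee decides are needed for participants already receiving PSL. Also exempt doses that the Investigator gives to eliminate an immediate hazard until the committee meets. Apart from that interim case, the taper decision stays with the committee, as the section intends.
3. State whether any dosing other than taper may continue during a halt. That choice is the sponsor's.

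No extra data, visits or staff are needed. The change must go through an amendment, and Section 10.11 records that this section was last revised to meet a regulator's requirement, so the new wording should remain consistent with that. The small downside is that a whole-study count may trigger a hold more often than a count within a smaller unit.
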